STUDY SETTING The WIHS, established in 1994, was a prospective cohort study of HIV disease progression in women from 9 US cities, in which HIV+ and HIV- participants are well-matched by age, race/ethnicity, education, and high-risk sexual and substance use behavior. 86,87 Semi-annual visits included in-depth interviews, physical exam, and collection of blood, oral, gynecologic, and urine specimens. Current visit structure is now annual in MWCCS. Interviews include sociodemographics, medical history (HIV- and non-HIV related), medication use, HAART use and adherence, substance use, and report of falls and fall-related injury, among others. A neurocognitive testing battery is performed every two years. 88,89 MWCCS has a central Data Analysis and Coordination Center (DACC) and an extensive repository of biological specimens. The Cannabis Research Laboratory, Columbia University Medical Center (CUMC), is directed by [name]. Her laboratory has been conducting federally-funded, placebo-controlled human laboratory studies of cannabis administration for the past 20 years, including studies with HIV+ research volunteers. By collaborating with [name], we have the opportunity to directly assess the acute effects of active vs inactive cannabis administration on a range of clinically-relevant outcome measures, thereby dissociating expectancy effects of cannabis from its pharmacological effects.

STUDY PARTICIPANTS.

We will recruit and test 60 women who report cannabis use within the past six months, including 30 HIV+ women and 30 demographically similar HIV- controls from the Bronx and Brooklyn MWCCS sites, and from clinical populations, such as patients receiving care at Einstein/Montefiore Medical Center, other medical facilities, referred by medical providers, or word-of-mouth if eligibility can be confirmed. Median age of Bronx MWCCS participants is 54 years, with 75% between 49 and 59 years. Inclusion Criteria: (1) current cannabis use (within 6 months) based on self-report, (2) able to perform study procedures, including ability to ambulate independently, (3) adequate hearing and vision, (4) for HIV+ women, use of stable HAART for at least 6 months. Participants must be willing to smoke cannabis during both study

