visits. Participants who use cannabis by vaping but are willing to smoke cannabis at the study visits will be allowed to enroll. Exclusion criteria: (1) pregnancy, (2) greater than occasional illicit drug use other than cannabis will be excluded; those with weekly or less frequent substance use will be enrolled but will be require to provide a negative urine drug test (other than cannabis) at each of the two study visits, (3) request for substance use treatment, (4) current parole or probation, (5) history of significant violent behavior within 12 months, (6) current uncontrolled major Axis I psychopathology requiring medical intervention (e.g. active psychosis, suicide risk,), or suicide attempt and/or suicidal ideation within 12 months (7) significant uncontrolled medical illness (such as late stage or metastatic cancer or on active treatment for cancer; chronic pulmonary disease on ventilator or continuous oxygen therapy); uncontrolled hypertension BP>160/100), (8) active heart disease within 12 months, (9) history of dementia, (10) severe hand tremor, (11) poor English fluency. All participants will be consented and compensated for their effort as approved by the IRBs of each participating institution (see Human Subjects).

RECRUITMENT. Established MWCCS research infrastructure and clinical populations will be used for study recruitment. In order to meet recruitment targets, electronic health records will be used to prescreen for eligibility in clinical populations. We have obtained a waiver to access records for recruitment purposes. Potential participants will be contacted via phone to provide initial information about the study and screen for eligibility, followed by an in-person screening visit and initial consent. Written informed consent will then be obtained in person prior to study enrollment.

RANDOMIZATION AND BLINDING. Each participant will smoke both inactive (0.0%) and active (7.0%) cannabis; the order in which each cannabis strength is administered will be counterbalanced and double-blind. Participants will be told that the strength of cannabis that they will smoke in each session will vary.

RESEARCH VISITS AND STUDY PROCEDURES

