Study Design (Table 1): A within-subject design will be used in which all participants will experience active and inactive cannabis, thereby increasing statistical power. Participants will be instructed to refrain from using any drugs for or tobacco cigarettes beginning at midnight prior to each session and to abstain from drinking alcohol for at least a 24-hour period prior to testing. A urine drug screen, breathalyzer, carbon monoxide (CO), and pregnancy test will be conducted upon arrival at the laboratory to confirm compliance. If there is evidence of illicit drug, alcohol, or cannabis use on the morning of the session based on CO, the session will be rescheduled. At the beginning of each session, a timeline follow-back questionnaire querying cannabis, alcohol, and other drug use will be completed. Participants will be offered a light breakfast (bagel or cereal, juice, coffee). Following breakfast, baseline cardiovascular measures (heart rate and blood pressure measurement), subjective effects questionnaires, and performance tasks will be completed. Tobacco cigarette smokers will be given up to two smoking breaks per session scheduled at the same time for both sessions in order to minimize nicotine withdrawal symptoms. The participant and study staff will be blind to cannabis cigarette content. Cardiovascular and subjective effects measures, mobility and balance testing, and a cognitive task battery will be completed at baseline and at 15–120 min intervals following cannabis administration. At the end of each session, participants will be carefully assessed to ensure they are no longer intoxicated, and may leave after passing field sobriety and balancing tasks. Participants unable to pass field sobriety testing will remain in the Research Laboratory until they are no longer intoxicated, pass repeat field sobriety testing, and can safely be discharged. They will be compensated for this additional time.

| Table 1 | Table 1. Time Course of Sessions | | | | | | | | | |
|---------|--|-----|--|--|--|--|--|--|--|--|
| Time | Event | | Event | | | | | | | |
| -60 | Begin session: urine toxicology, CO, breathalyzer, pregnancy testing timeline flow-back questionnaire, breakfast | 105 | Vitals, subjective effects, MRF, mobility, balance and cognitive batteries | | | | | | | |
| -30 | Field sobriety, vitals, subjective effects, mobility, balance and cognitive batteries | | | | | | | | | |

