Task: Participant are presented with an 18 (columns) x 16 (rows) matrix. Odd rows contain symbols, even rows contain empty answer boxes (18x8 = 144). The task is to translate the symbols into digits with the help of a provided key within a 2 min time frame.

Main outcomes: (1) Total number of correct responses; (2) Total number of incorrect responses

(3) Behavioral Pattern Separation Task – Object Version (BPS-O)

Length of time: 12 minutes

Measures: Recognition Memory

Task: Participants participate in a 2-part experiment to assess recognition memory.

The first part of the experiment presents 128 pictures (default) of everyday items and participants have to decide whether the item is an OUTDOOR or an INDOOR item. The second part of the experiment presents 64 of the previously seen pictures (targets), 64 of very similar items (lures), and 64 new items (foils). Participants are asked to categorize the items as old, new, or similar within 2.5s (default).

Main outcome: Percent correct

(4) Stroop Task: Color **Length of time:** 3 minutes

Measures: Reaction Time/Response Inhibition

Task: Participants are given color words written in color and are asked to indicate the color of the word

(not its meaning) by key press as fast as they can without making too many errors.

Congruent trials: color word and the color it is presented in are the same Incongruent trials: color word and the color it is presented in are not the same

Control trials: colored rectangles

Main outcomes:

- 1) overall proportion correct of all trials
- 2) overall mean latency (in ms) of all correct trials
- 3) mean latency of all correct congruent trials (in ms)
- 4) mean latency of all correct incongruent trials (in ms)
- 5) mean latency of all correct control trials (in ms)
- 6) proportion correct of congruent trials
- 7) proportion correct of all incongruent trials
- 8) proportion correct of all control trials
- e. Cannabis Administration: Inactive and active cannabis cigarettes (0.0%, 7.0% Δ^9 THC) provided by the National Institute on Drug Abuse have leaves that differ slightly in color. One cigarette end is placed in a plastic cigarette

| Year 1 | | | | Year 2 | | | |
|--------|----|--------|--------|--------|-----------|---------------|--|
| | | | | | | | |
| | | | | | | | |
| | | | | | | | |
| | | | | | | | |
| | | | | | | | |
| | | | Г | | | | |
| | | | | | | | |
| | Ye | Year 1 | Year 1 | Year 1 | Year 1 Ye | Year 1 Year 2 | |

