holder, and the exposed end pinched to cover the leaves. Cannabis is administered using a standardized cued-smoking procedure, which produces reliable increases in heart rate and plasma Δ^9 - THC. Participants will be instructed to 'light the cigarette' (30 sec), 'get ready' (5 sec), 'inhale' (5 sec), 'hold smoke in lungs' (10 sec) and 'exhale.' Participants will smoke 1 puff/minute in this manner, with a 40-sec interval between each puff until 50% of the cigarette has been smoked. Cigarettes are stored frozen in an airtight container and humidified at room temperature for 24 hours before use.

PROPOSED TIMELINE. Table 2 depicts the timeline for recruitment and testing. Recruitment in the first quarter of Year 1 will be lower to account for study planning and initiation. Each participant will complete two study visits (minimum 48 hours apart) for a total of 120 visits. In the final 2 quarters, we will complete data collection, final reliability checks and statistical analyses, write manuscripts, and submit an R01 application.

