7. DATA ANALYSIS

OVERVIEW AND APPROACH: To determine the acute effects of cannabis on balance, mobility, and cognition among older HIV+ and HIV- women.

OUTCOMES: Primary outcomes are functional reach and gait speed (Aim 1) and number of correct suppressions on the Sustained Attention to Response Task (SART) (Aim 2) under active and inactive cannabis

STATISTICAL ANALYSIS: Descriptive data analysis will identify erroneous values, outliers, distributional properties, and insufficient data dispersion for making analytic comparisons. As needed, transformations such as logarithmic or categorization will be applied to skewed continuous variables. The HIV+ and HIV-arms will be compared using t-tests/ANOVA, and/or rank tests for continuous and exact tests for binary baseline covariates to identify potential confounders and generalizability issues. Within our crossover design for the outcomes of both Aims 1 and 2 with each subject getting both active and inactive cannabis (after verifying distributions are not too skewed for normal approximation), we will use linear mixed effects models, which take account of correlations among measurements within the same subjects, to compare functional reach and gait speed (Aim 1) and number of correct suppressions on the Sustained Attention to Response Task (SART) (Aim 2) after inactive vs. active cannabis administration, and to evaluate whether HIV+ women have greater declines in gait speed and functional reach and attention than HIV- women, after administration of active vs. inactive cannabis (i.e. by fitting interaction terms). In these models the 15, 60, 105 and 150 minute measures with baseline from the same visit subtracted will be the outcome(s). Because peak marijuana effect is expected to occur on 15 to 60 minutes, for the

purpose of effect size estimation, averaged 15 and 60 minute results (with baseline subtracted) will be the primary outcome(s) and this analysis reduces to a two way ANOVA or equivalently two sample t-test of differences in differences. Other quantitative and descriptive approaches previously applied to these measures¹⁰⁴ including area under the curve and trajectories will be fit.

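### Drug order is not tied to HIV status and the analysis names no period term, so a chance order imbalance between HIV+ and HIV- women would go straight into the main contrast

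*Combined protocol and SAP*

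**What the plan says.** Section 2 of the combined protocol and SAP has a paragraph headed "RANDOMIZATION AND BLINDING". Its one statement on drug order is that "the order in which each cannabis strength is administered will be counterbalanced and double-blind". It does not say how the order list is made, whether order is balanced within each HIV group, how the list is concealed or who holds it. The Latin square described under mobility testing covers the three walking and reciting conditions, not the drug.

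The sample is 60 women, "including 30 HIV+ women and 30 demographically similar HIV- controls". On periods: "Each participant will complete two study visits (minimum 48 hours apart) for a total of 120 visits". Each woman is therefore either active-first or inactive-first.

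Section 7 (Data Analysis) uses mixed models with interaction terms "to evaluate whether HIV+ women have greater declines in gait speed and functional reach and attention than HIV- women". The primary outcome is the mean of the 15 and 60 minute values minus the same-visit baseline. The authors note that the analysis then reduces to a two-sample t-test of differences in differences. They name HIV status, cannabis and their interaction, but no period or sequence term.

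**The concern.** In a two-period crossover, each woman's active-minus-inactive difference also carries the visit effect, with a sign set by her order. That effect cancels from the HIV contrast only if the share of active-first women is the same in both HIV groups. Balance over all 60 women does not secure this.

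Subtracting the same-visit baseline removes a constant shift between visits. It does not remove a difference between visits in how performance changes within the session, for example through practice, novelty or fatigue. Such a difference is plausible, because the full battery is run at baseline and four more times in each session.

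The HIV-by-cannabis contrast is the question in both aims. With order not tied to HIV status and no period term named, nothing in the written plan protects that contrast from a chance order imbalance.

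**Working it through.** **The plan's own figures, used here as a yardstick.** The plan states no figure for order balance. Section 7 gives correlations of 0.82 (walking time) and 0.87 (functional reach).
- Variance of the mean of two post values minus baseline = 1.5(1 - rho) sigma². This gives 0.27 and 0.195, as stated.
- Active-minus-inactive has twice that variance: 0.54 and 0.39 sigma².
- Detectable HIV difference at two-sided alpha 0.05 and 80% power = 2.80 x sqrt(0.54) x sqrt(2/30) = 0.53 for walking, and 2.80 x sqrt(0.39) x sqrt(2/30) = 0.45 for reach.
- The plan states 0.63 and 0.53, which match 90% power (t-test: 0.626 and 0.532). Its alpha 0.25 pair, 0.38 and 0.32, reproduces at 80% power. That mismatch is a separate matter.

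**Chance of imbalance.** Suppose order is balanced 30/30 overall but not by HIV group. The number of active-first HIV+ women, X, is then hypergeometric (60, 30, 30), and the gap between groups is |2X - 30|.
- Gap 0: 20%.
- Gap 4 or more: 44%. Gap 6 or more (18 v 12): 20%. Gap 8 or more: 7%.
- Gap of exactly 2: 100 - 20 - 44 = 36%, so the median gap is 2 (16 v 14).
- Under simple randomisation instead: 10% exact balance, and 37%, 16% and 5% for gaps of at least 4, 6 and 8.

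**Size of the shift.** Let d be the visit 2 minus visit 1 difference in within-session change, and p the active-first share in a group. The group mean of active-minus-inactive is the drug effect plus d(1 - 2p). The HIV contrast is therefore shifted by 2 x (difference in p) x d.
- Median gap: 2 x 2/30 = 0.13 d.
- 18 v 12: 2 x 6/30 = 0.40 d.

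The documents give no value for d, so a range is assumed. Type I error is simulated with 4,000 runs per cell; pairs are walking, reach.

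| Assumed d (sigma) | Shift at 16 v 14 | Shift at 18 v 12 | Unadjusted type I error at 18 v 12 | Unadjusted type I error at 15:15 in each group |
|---|---|---|---|---|
| 0.1 | 0.01 | 0.04 | 0.050, 0.058 | 0.047, 0.047 |
| 0.25 | 0.03 | 0.10 | 0.068, 0.073 | 0.041, 0.035 |
| 0.5 | 0.07 | 0.20 | 0.093, 0.099 | 0.017, 0.013 |

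With an order term, type I error is about 0.05 in every cell. Averaged over all allocations balanced 30/30 overall, the unadjusted test also stays at about 0.05 (0.049 to 0.055). The last column is conservative because the visit effect remains in the residual variance after it has cancelled from the contrast.

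**Lost precision.** The SD of the difference in active-first share is 0.130, so the shift has variance 4 x 0.130² x d² = 0.068 d². The sampling variance of the contrast is 2 x 0.39/30 = 0.026 sigma² for reach and 2 x 0.54/30 = 0.036 sigma² for walking.
- At d = 0.25: 0.0042/0.026 = 16% extra variance for reach, and 0.0042/0.036 = 12% for walking.
- At d = 0.1: about 3% and 2%.

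**Cost of adjusting.** At 18/12 v 12/18, the standard error with an order term rises by 1/sqrt(1 - 0.2²) = 1.021.

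**The case against.** Three objections carry weight.

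First, the gap is one of description. The paragraph is headed as randomization, and counterbalanced may already mean equal orders within each HIV group. A reader might infer that order is not randomised at all; the documents do not say so. If order is already balanced by HIV status, one sentence settles the allocation part of this point.

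Second, a reader might infer that order alternates by enrolment, so that staff can predict it. Nothing in the documents mentions alternation or a list visible to testers. They state that "The participant and study staff will be blind to cannabis cigarette content". The two strengths "have leaves that differ slightly in color", but the cigarette ends are covered to hide this. Recognising intoxication at visit 1 would reveal the same woman's visit 2 under any two-period scheme. Predictability is therefore no part of the finding.

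Third, the harm is modest. A reader might infer an inflated false-positive rate, but averaged over random unstratified allocations the rate stays at about 0.05. Pairing a gap of 8 women (a 7% event) with d = 0.5 sigma gives 2 x 8/30 x 0.5 = 0.27 sigma, but that is a corner case. The change SDs are sqrt(0.195) = 0.44 and sqrt(0.27) = 0.52 sigma, so a visit effect of 0.5 sigma is about one full SD of change. At the median gap the shift is 0.07 sigma or less over the whole assumed range.

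Section 9 also calls this a pilot that is not fully powered for group differences. That lowers the stakes for testing. But section 7 gives effect-size estimation as the purpose of the primary summary, and an avoidable shift in that estimate still matters.

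**Conclusion.** The point holds as a gap in design and analysis of modest size. The plan does not tie drug order to HIV status and names no period term, while its main contrast is between HIV groups. If balance is only overall, four allocations in five are unequal by HIV group and one in five is at least as unequal as 18 v 12. At that split, the contrast shifts by 0.04 to 0.20 sigma for assumed visit effects of 0.1 to 0.5 sigma, against stated detectable effects of 0.53 and 0.63.

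This is error conditional on the allocation realised, together with some lost precision. It does not show that order is non-random or predictable, or that the test is invalid on average.

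The conclusion rests on two assumptions: that counterbalancing does not already operate within HIV group, and that within-session change differs between visits. The documents settle neither. The sigma figures apply to walking time and functional reach. The plan has no normative data for the attention task, so only the multipliers (0.13, 0.40) carry over to it.

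**What to change.** Make two changes together.

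1. In section 2, state that order (active-first or inactive-first) is assigned by computer-generated permuted blocks of varying size, separately for HIV+ and HIV- women, with a target of 15:15 in each group. The list is held by someone who does not run sessions. Varying sizes are preferable because small fixed blocks can be guessed if earlier orders become known: 75%, 71% and 68% correct for blocks of 2, 4 and 6.
2. In section 7, add period (visit) to the mixed model. In the difference-in-differences form, this is an order covariate.

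Each change covers what the other leaves. Stratified balance without the period term makes the t-test conservative, and dropout, for which no rate is given, can break the balance. A common period term without stratified balance does not remove a visit effect that itself differs by HIV status, whereas 15:15 in each group does.

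The cost is two short lists made once, one degree of freedom, and about 2% in standard error if the split ends at 18/12 v 12/18. Sample size, visits and procedures are unchanged.

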| 0 | Cannabis administration | 150 | Vitals, subjective effects, MRF, mobility, balance and cognitive batteries | | | | | | | |
| 15 | Vitals, MRF (Marijuana Rating Form), subjective effects, mobility, balance and cognitive batteries | 180 | Lunch/snacks | | | | | | | |

| 60 | Vitals, MRF, subjective effects, mobility, balance and cognitive batteries | 210 | Field sobriety, end session | |
|----|--|-----|-----------------------------|--|
|----|--|-----|-----------------------------|--|

- **a.** Behavioral Measurements: (1) Subjective Effects Ratings: A 3-minute series of visual analog scales (VAS) in which participants indicate how they are feeling at that moment will be done 4 times over the course of the study visit. This 44-item scale assesses the effects of cannabis on a range of affective and physical symptoms (e.g., friendly, mellow, sedated, anxious).⁹⁰ (2) Marijuana Rating Form: Cannabis-related effects are assessed using a five-item visual analog scale asking participants to rate the strength of the cannabis effect, good effect, bad effect, drug liking, and willingness to smoke the cannabis again. Participants also indicate whether they think cannabis is active or inactive.
- **b.** Mobility testing: Timed gait and Walking While Talking (WWT). Gait speed is measured under normal walking and attention-demanding conditions. There are two single task conditions: 1) Normal Walk (NW): participants are asked to walk 20 ft at their "normal pace" and are timed; and 2) Cognitive (Alpha): participants stand still while reciting alternate letters of the alphabet starting with the letter B for 30-sec out loud. In WWT, participants walk 20 ft at their normal pace while reciting alternate letters of the alphabet starting with the letter 'B' and are instructed to pay equal attention to both tasks.^{28,91} The three test conditions are presented in a counterbalanced order using a Latin-square design. Reliability and validity for this walking paradigm have been established.^{30,92} The main comparison is between NW and WWT; cognitive performance is also quantified with the number of correct letters and errors generated.⁹³⁻⁹⁵

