POWER CALCULATIONS: Under the standard approach to power estimation of hypothesis testing at a two sided α =0.05 with β =0.2, this study even with only 60 subjects is powered to detect (active vs. inactive cannabis) effect sizes of at least 0.53 for functional reach and 0.63 for walking time, both of which are considered to be medium. The power here is greatly increased by repeated measures being taken pre and post administration with the outcome being the difference of averaged measures that from our normative data have correlations of ρ =0.82 an 0.87 for walking time and functional reach which reduces the variances of within subject difference to 0.27 σ 2 and 0.195 σ 2 respectively. We do not have similar normative data for power estimation of other outcomes. Some authors believe that in pilot studies that will be later confirmed 105-107 a higher α =0.25 is appropriate, in which case, the detectable effect sizes drop to 0.32 for reach and 0.38 for walking time which are considered close to small. Other criteria besides hypotheses testing that are satisfied by smaller sample sizes should be considered for pilot studies 107-109 with other authors finding 20-70 subjects adequate for estimating standard deviations 110-112 and effect sizes 112,113 of outcomes and identification of subject exclusion criteria for the main study.

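### Recitation during Walking While Talking is scored as raw counts, so this secondary cognitive measure depends on how long the 20-ft walk takes

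*Combined protocol and SAP*

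**What the plan says.** Section 2, Mobility testing, describes three conditions: normal walking (NW), standing recitation (called Alpha), and WWT.

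- Alpha: "participants stand still while reciting alternate letters of the alphabet starting with the letter B for 30-sec out loud". The window is fixed.
- WWT: "In WWT, participants walk 20 ft at their normal pace while reciting alternate letters of the alphabet". The only limit on recitation is the length of the walk. Women are told to divide their attention evenly between the two tasks.
- Scoring: "The main comparison is between NW and WWT", and "cognitive performance is also quantified with the number of correct letters and errors generated".

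The same section says that gait speed is measured in both the normal and the attention-demanding walk, so WWT walking time is available.

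Section 7, Data Analysis, does not mention the letter or error counts. It states: "Primary outcomes are functional reach and gait speed (Aim 1) and number of correct suppressions" on the Sustained Attention to Response Task (SART). Its models are meant "to evaluate whether HIV+ women have greater declines in gait speed and functional reach and attention than HIV- women", comparing active with inactive cannabis. The power paragraph says that there are no normative data for outcomes other than walking time and functional reach.

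**The concern.** A count collected over a window that varies is a rate multiplied by a duration. For WWT the duration is the walking time, and walking time is what cannabis is expected to change. A woman who walks more slowly in the active session has longer to recite. She can produce more letters, and more errors, without any change in how well she recites.

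Recitation shows whether a woman who slowed down was protecting her speech or was losing ground on both tasks. A raw count mixes those two cases. In the active session it could suggest that recitation held up when letters per second had fallen.

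The unequal windows raise a second problem. Alpha and WWT letters would be scored by the same count over very different times, so any comparison of the two on raw counts would mostly reflect the length of the windows.

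**Working it through.** The plan gives no figure for the letter score, so there is none to reproduce.

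**Inputs from the protocol.** Walk length D = 20 ft = 20 × 0.3048 = 6.096 m. Alpha window = 30 s. Scores are raw counts.

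**Assumptions.** WWT speed v is 0.5 to 1.2 m/s. The mean letter rate is r per second. Recitation starts and stops with the walk. The documents give none of these.

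**Step 1: the windows.** WWT time = D / v.

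- At 1.2 m/s: 6.096 / 1.2 = 5.08 s, and 30 / 5.08 = 5.9.
- At 0.5 m/s: 6.096 / 0.5 = 12.19 s, and 30 / 12.19 = 2.5.

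At the same letter rate, Alpha would yield 2.5 to 5.9 times as many letters as WWT with no divided-attention cost.

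**Step 2: effect of slowing on the WWT count.** Expected count = r × D / v. If speed falls by a fraction s and letter rate by a fraction f,

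change in count = (1 − f) / (1 − s) − 1.

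D, the starting speed and the starting rate all cancel, so the percentages do not depend on the assumed values.

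| Fall in speed | Fall in letter rate | Change in correct-letter count |
|---|---|---|
| 10% | 0% | 1/0.90 − 1 = +11.1% |
| 15% | 0% | 1/0.85 − 1 = +17.6% |
| 20% | 0% | 1/0.80 − 1 = +25.0% |
| 20% | 10% | 0.90/0.80 − 1 = +12.5% |
| 20% | 20% | 0.80/0.80 − 1 = 0% |
| 20% | 30% | 0.70/0.80 − 1 = −12.5% |

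The count falls only when letter rate drops by a larger fraction than speed. Errors follow the same formula with the error rate in place of r. At an unchanged error rate they also rise by 11%, 18% or 25%.

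**Step 3: size in letters.** At an assumed 1.0 m/s and 1 letter per second, the starting count is 6.1. A 10% fall in speed gives 6.8 and a 20% fall gives 7.6, a gain of 0.7 to 1.5 letters.

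**Step 4: does the design remove it?** The crossover does not, because the slowing is expected in the active session. Subtracting the same-visit baseline, as section 7 does for the primary outcomes, would not either. The baseline walk comes before smoking, so the change in walking time stays in the difference. The plan does not say whether letter counts would be analysed in this way.

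**Step 5: the score after the fix.** Count divided by walking time is r. A change in speed alone then gives 0% change. A 10% fall in letter rate with a 20% fall in speed appears as −10%, where the raw count shows +12.5%.

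**The case against.** The strongest objection is about scope, and most of it stands. The letter count is an additional descriptor with no hypothesis, model or power attached. The dual-task effect on mobility is read from gait over the same 20 ft in both walks, and attention is tested by the SART. A reader might infer that raw counts hide the dual-task cost that Aim 1 looks for. The documents do not support that: Aim 1's primary outcomes are functional reach and gait speed, neither uses letters, and slowing under WWT would show directly in gait.

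Other points on this side also stand:

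- A reader might infer that slowing always raises the score. It does so only at an unchanged letter rate. Errors rise too, so the pair of counts need not look favourable, and the ratio of correct letters to errors does not depend on walking time.
- No comparison of Alpha letters with WWT letters is stated, so the 2.5 to 5.9 ratio is a warning about a natural use of the data. It is not an error in a planned test. Alpha alone, active against inactive, has a fixed window and no such problem.
- The documents give no figure for acute slowing, and none for WWT speed by HIV status. A claim that the count favours HIV+ women is therefore not established.
- A reader might extend the point to the Stroop task because no interference score is listed. That is a different matter. Congruent, incongruent and control latencies are listed separately, so general slowing would be visible and interference is a simple subtraction.

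The scoring sentence cites earlier papers that may use a rate. The protocol does not say so, and its stated rule is a count.

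**Conclusion.** The point holds within limits. Scored as written, the WWT letter and error counts depend on walking time, which the plan expects active cannabis to lengthen. At unchanged rates, speed falls of 10% to 20% inflate both counts by 11% to 25%, and an equal proportional fall in letter rate disappears from the correct-letter count. The inflation percentages are arithmetic and need only that recitation lasts as long as the walk. The window of about 5 to 12 s rests on assumed speeds, and the actual amount of slowing is unknown.

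The consequence is confined to the secondary cognitive component of WWT. The primary outcomes, their power statement and the NW-WWT gait comparison are unaffected. It is still worth correcting before analysis, because a better score can be computed from data already collected.

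**What to change.** In section 2, Mobility testing, define the WWT recitation scores as correct letters per second and errors per second, dividing each count by the WWT walking time at that assessment. Score Alpha on the same scale by dividing by 30 s. State that any comparison of WWT with Alpha recitation will use these rates at the same time point, for example as the WWT rate relative to the Alpha rate. Repeat the definitions in section 7 and label the measures secondary. Raw counts can still be reported beside the rates.

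Confirm in the procedures that recitation is counted only while the walk is being timed. The cost is a few sentences of scoring definition. No new data, visits or testing time are needed, and no primary analysis changes.
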